9 STUDY POPULATION

9.1 SUBJECT ACCOUNTABILITY

A listing of subject disposition and ralinepag exposure will include the subject number, treatment group in the parent study, first and last ralinepag dose date/time in the APD811-007 study, date completed/discontinued the study, study drug exposure (weeks), reason for discontinuation, and any other details regarding reason for discontinuation. The summary of subject accountability will include the number (percent) of subjects who completed the study without early termination, the number of subjects who completed ralinepag treatment by each visit achieved, number of subjects who discontinued ralinepag treatment, and the reason for discontinuation. This summary will be provided by treatment group in the parent study and overall.

Ralinepag exposure and the total patient-years of ralinepag exposure will be summarized by the treatment group in the parent study and overall. Duration of treatment will be further characterized by weeks on the immediate-release and extended-release formulations.

In addition, for subjects who were in the ralinepag group of the parent study, exposure to ralinepag in the parent study will be combined into the APD811-007 study. The overall exposure to ralinepag across both the parent study and the APD811-007 study will be summarized.

9.2 ELIGIBILITY CRITERIA

The listing of entry criteria for all subjects will include whether the subject rolled over from the previous study, each subject's treatment group in the parent study, status regarding meeting all eligibility criteria (yes/no), and an explanation if all eligibility criteria are not met. The summary of entry criteria will include the number (percent) of subjects who met all eligibility criteria and the number (percent) of subjects who did not meet all eligibility criteria by treatment group in the parent study and overall.

In addition, a listing will be provided for protocol deviations. The listing will include the subject number, deviation date, deviation type, deviation severity, and deviation description by treatment group in the parent study.

9.3 OTHER DESCRIPTIONS OF STUDY POPULATION

9.3.1 Demographics

The listing of subject demographics will be organized by treatment group in the parent study, and will include subject number, country, assessment date, date of birth, age (years), sex, ethnicity, race, height, weight, and body mass index. The age will be calculated based on the first ralinepag dose date in the APD811-007 study. The summary of demographics will include descriptive statistics for age (years), height, weight, and body mass index at first dose of ralinepag, where weight and height are obtained from the parent study; and categorical summaries for age (<65 and ≥65 years), sex, ethnicity, and race.

9.3.2 Baseline Characteristics

Baseline characteristics including 6MWD, 6MWD category (≤440 m versus >440 m), pulmonary vascular resistance (PVR), WHO FC, BNP, and NT-proBNP will be summarized by treatment group in the parent study and overall. Baseline measures are defined as the last measurement prior to the first ralinepag dose in the APD811-007 study.

9.3.3 PAH History

The listing of PAH history will be organized by treatment group in the parent study, and will include the subject number, the date of initial PAH diagnosis, number of years since PAH diagnosis, PAH classification, WHO FC at Baseline, 6MWD at Baseline, PVR at Baseline, PAH disease specific concomitant medication, and background PAH medication name. The number of years since PAH diagnosis will be calculated based on the first ralinepag dose date in the APD811-007 study. The summary of PAH history will include descriptive statistics for years since PAH diagnosis and categorical summaries for PAH classification and PAH disease specific concomitant medication at randomization in the parent study.

9.3.4 Concomitant Medications

The listing of concomitant medications will be organized by treatment group in the parent study and will include the verbatim term, WHO Drug Dictionary standard name, the date started, date discontinued, and the condition(s) treated/indication(s). Summaries will be provided for medications ongoing from the parent study and for those added in the APD811-007 study. Each summary will be provided by treatment group in the parent study and overall and will include the

number (percent) of subjects reporting each medication by WHO Drug Dictionary medication name.

9.3.5 Ralinepag Dosing

In the APD811-007 study, a listing and a summary will be provided for ralinepag dosing. The listing will be organized by treatment group in the parent study, and will include the subject number, visit date, titration action, actual dose, immediate-release or extended-release, and total daily dose.

The ralinepag dose will be summarized by analysis visit. The summary will also include the number (percent) of subjects in each dose category by treatment group in parent study and overall.

10 EFFICACY ANALYSES

10.1 TIME TO CLINICAL WORSENING

Time to the first event of clinical worsening will be calculated and listed. Time to clinical worsening is calculated from the treatment start date in APD811-007 to the first occurrence of clinical worsening. For subjects who do not experience clinical worsening, it will be censored at the last record date of clinical worsening assessment or end of study, whichever is latest.

Summaries and analyses will be performed for time to clinical worsening. Kaplan-Meier estimate will be provided along with the corresponding p-value using log-rank test. In addition, hazard ratio, 95% confidence interval, and p-value will be provided using the Cox proportional hazard model. A Kaplan-Meier plot will also be provided.

10.2 6-MINUTE WALK TEST

The listing of the 6MWT will be organized by treatment group in the parent study, and will include the subject number, visit, assessment date/time (day), last ralinepag dose date/time (day), the last ralinepag dose (micrograms), hours from last ralinepag dose to 6MWT, 6MWD results, and use of supplemental oxygen. The summaries of 6MWD will be provided by treatment group in the parent study for each visit. The summaries will include descriptive statistics for 6MWD and the change from baseline. Baseline is defined as the last 6MWD measured prior to the first dose of ralinepag in the APD811-007 study.

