6.12.9 Follow-up of Adverse Events Present at Last Scheduled Study Visit

The AEs present at the last study day (End of Study) that require follow up or a repeat laboratory test will be followed up initially for 30 days according to the Sponsor's. AEs that have not resolved or stabilized at 30 days after the last subject's last study dose will be reviewed on an individual basis to determine whether the database will be locked and subsequently updated once the events of ongoing AEs are resolved or whether database lock will be held.

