6.14.1 Handling of Withdrawals

Although a subject is not obliged to give his/her reason for withdrawing prematurely, the Investigator will make a reasonable effort to obtain the reason while fully respecting the subject's rights. If there is a medical reason for discontinuation, the subject will remain under the supervision of the study physician until in satisfactory health. Reasonable efforts will be made to contact a subject who fails to attend any follow-up appointments, in order to ensure that he/she is in satisfactory health.

If a subject is prematurely discontinued from this study, every attempt will be made to follow the End of Study Procedures described in Section 7.

In addition, all subjects will be contacted at the time of Study APD811-007 closure to assess vital (mortality) status. The vital status follow-up contact of subjects will depend on local regulations or specific agreement with the subject and Investigator.

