6.15 ALLOWABLE VISIT AND PROCEDURE WINDOWS

A ± 3 -day window is allowed for study visits and procedures during the Dose Titration Period, Treatment Period, and End of Study and Follow-up Visits, with the exception of the Q3 Month Visits during the Treatment Period, which are allowed a ± 5 -day window.

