7.2 STUDY PROCEDURES

7.2.1 *Baseline Study Procedures – All Subjects*

Subjects who meet all the entry criteria and are eligible for the study will report to the clinical study unit to confirm eligibility for the study and complete all Baseline procedures and receive study drug and instructions. The study drug will be given in the morning at the study site during the Baseline Visit.

7.2.1.1 *Pre-baseline Procedures*

All Week 25 measurements from Study APD811-003 will serve as Baseline assessments for Study APD811-007.

Placebo-treated subjects who discontinued prematurely from Study APD811-003 due to clinical worsening are permitted to enroll in APD811-007 provided that all end of study procedures are performed per the ADP811-003 protocol. For these subjects, the time of the clinical worsening event that led to early termination in Study APD811-003 will serve as the Baseline time point for clinical worsening in APD811-007.

Any unresolved AE from Study APD811-003 will be carried forward and recorded.

7.2.1.2 *Baseline Procedures*

- Medical history (partial history, to update findings from Study APD811-003)
- Physical exam¹
- 12-lead ECG¹
- Clinical laboratory tests (to include hematology, coagulation parameters, serum chemistry, and urinalysis)¹
- Serum pregnancy test (women only)¹
- Vital signs¹
- 6MWT¹
- BNP/NT-proBNP¹
- Assessment of clinical worsening

- WHO/NYHA FC assessment¹
- Record AEs¹
- Record concomitant medications¹

¹ Taken from Week 25 Visit in Study APD811-003

7.2.2 Study Procedures – for Immediate-release Dose Titration Period (Study APD811-003 Placebo Subjects)

Visits after Baseline should occur weekly for each escalation of study drug dose. There should be 1 study visit per week during the Dose Titration Period. Beyond the weekly visit, any additional visit during the Dose Titration Period will be documented as an ‘unscheduled’ visit.

If a subject reaches a stable MTD and no further dose escalations are planned, the Dose Titration Period will be considered completed and will be followed by monthly assessments for the first 3 months and then every 3 months until the subject is discontinued from the study, Sponsor termination of the study, or the last subject enrolled completes approximately 6 months of treatment with ralinepag.

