8.2 PREMATURE DISCONTINUATION AND MISSING DATA

A subject may voluntarily withdraw or be withdrawn from the study by the Investigator at any time for reasons including the following:

- Clinical worsening
- Deviation/noncompliance with the protocol
- A serious or intolerable AE occurs
- The Sponsor or Investigator terminates the study, or
- Withdrawal of consent – any subject may withdraw his/her consent from the study at any time. The Investigator should make a reasonable attempt to document the specific reason why consent is withdrawn.

All available data from all subjects in the Safety Population, as defined in Section 7, will be used as detailed in this analysis plan. Missing data will not be imputed.

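### Does SAP 10.1 bias the clinical worsening curve by censoring at the later of the last assessment and an undefined end of study?

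*SAP*

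**What the plan says.** SAP 10.1 measures time to clinical worsening from the treatment start date in APD811-007 to the first event. For a subject with no event, "it will be censored at the last record date of clinical worsening assessment or end of study, whichever is latest". The date feeds the Kaplan-Meier estimate, the log-rank test and the Cox hazard ratio.

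SAP 10.1 does not define *end of study* and does not refer to the subject-level date in the SAP 9.1 disposition listing, "date completed/discontinued the study".

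The protocol uses the term in these places:
- **Tables 1 and 2:** End of Study is a visit column with its own worsening assessment, followed by a 28-day follow-up that also has one. Sections 7.2.4 and 7.2.5 repeat this for all subjects.
- **Section 6.12.9:** "The AEs present at the last study day (End of Study) that require follow up".
- **Section 6.14.1, for early leavers:** "every attempt will be made to follow the End of Study Procedures described in Section 7".
- **Section 6.15, on visit windows:** "End of Study and Follow-up Visits".
- **Section 7.2.1.1, lower case, for placebo subjects who left the parent study early:** "all end of study procedures are performed per the ADP811-003 protocol".

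For the calendar end, Section 6.14.1 uses another word: "all subjects will be contacted at the time of Study APD811-007 closure to assess vital (mortality) status".

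**The concern.** A later-of rule moves a subject's censoring date beyond the last worsening assessment only when the other date is later. Relative to that assessment, it can only add event-free time. How much it adds depends on a term that the SAP leaves undefined.

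If a programmer took *end of study* to be trial closure, a subject who left event-free in the first year would be counted as at risk and event-free until the trial ended. The original protocol is dated June 2014 and Amendment 4 May 2019, so this could mean years. No worsening assessment is planned after the 28-day follow-up, and SAP 12 states that follow-up vital status was not collected. Later events in leavers could not be seen, and the curve would look too favourable.

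Clinical worsening is a secondary objective of the protocol, and the same dates enter the comparison of the parent-study groups.

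**Working it through.** **1. Which date is meant.** Every use of the term found for this trial or its parent is a visit or procedure set that a subject undergoes. The shape of the sentence agrees. If the term meant closure, it would fall at or after nearly every assessment, and the other branch would be almost idle. On the subject-level reading both branches work. A subject who completes the 28-day follow-up is censored at that later, observed contact. A leaver with no exit assessment is censored at exit.

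**2. Whether time up to exit is really observed.** Protocol 6.9 has the investigator evaluate worsening throughout the study. Section 6.12.1 monitors adverse events to 30 days after the last dose, and 6.13 records concomitant drugs with dates. Deaths, hospitalisations and added PAH drugs can therefore be captured between visits. The combined criterion (walk distance, functional class and right heart failure) is the main part that needs a visit.

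**3. Inputs.** The plan has no figure to reproduce: it states no event or exit rate, and SAP 6 reports no sample size calculation. Assumed: constant worsening hazard L = 0.05 to 0.20 per year and constant, independent event-free exit hazard D = 0.02 to 0.25 per year. True worsening by time t is 1 − exp(−Lt).

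**4. Subject-level reading.** If events are known up to exit, the bias is zero. As a harsh case, credit a share p of leavers with g = 0.125 years (1.5 months) in which no event could be detected. The estimated cumulative hazard is the integral of L·a/(a + p·c), where a(s) = exp(−(L+D)s) and c(s) is the proportion who left event-free in the last g years. After the first g years, c/a = D/(L+D) × (exp((L+D)g) − 1).

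Example with L = 0.10, D = 0.05, p = 1, t = 3: c/a = (1/3) × (exp(0.01875) − 1) = 0.0063. The hazard is about 0.30/1.0063 = 0.2981, so event-free is 74.22% against a true 74.08%, a bias of 0.14 points.

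**5. Closure reading.** Reported worsening = L/(L+D) × (1 − exp(−(L+D)t)). Same example: (0.10/0.15) × (1 − exp(−0.45)) = 24.16%, against 1 − exp(−0.30) = 25.92%, a bias of 1.76 points.

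| L, D per year | Own exit, p = 1 | Own exit, p = 0.2 | Closure |
|---|---|---|---|
| 0.05, 0.02 | 0.03 | 0.01 | 0.40 |
| 0.10, 0.05 | 0.14 | 0.03 | 1.76 |
| 0.10, 0.10 | 0.27 | 0.05 | 3.36 |
| 0.20, 0.25 | 1.01 | 0.21 | 12.2 |

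Entries are points by which 3-year worsening is understated. For scale, the standard error with 60 subjects, 74.1% event-free and no censoring is √(0.741 × 0.259/60) = 5.7 points.

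**6. Check by simulation.** With L = 0.10 (true 3-year worsening 25.9%), D = 0.02, 0.05, 0.10, 0.25 and events known up to exit:
- own-exit censoring: 25.9, 26.0, 25.9, 25.9%
- censoring at the last quarterly visit: 25.9, 26.1, 26.2, 26.6%
- closure: 25.1, 24.2, 22.5, 18.5%

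A second simulation used staggered entry, yearly risks of 5 to 20% for worsening and for exit, and no events captured after the last assessment. Relative to censoring at that assessment, own exit lowered the 3-year figure by 0.1 to 0.9 points and closure by 1.1 to 12.9.

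**7. Hazard ratio under closure.** With a true ratio of 1, L = 0.15 and closure at 3 years, the Cox estimate is about 0.95 for exit of 0.05 against 0.02 per year, 0.93 for 0.10 against 0.05, and 0.87 for 0.20 against 0.10. Equal exit does not fully protect it. With a true ratio of 2 (0.20 against 0.10) and exit of 0.25 in both groups, the estimate is about 1.95 with closure at 3 years and 1.9 at 5. With a true ratio of 1, own-exit censoring gives about 1.00 throughout.

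**The case for a change.** The best case for a change is that it is cheap and the error would be one-sided. The synopsis has all ongoing subjects complete the End of Study Visit when the Sponsor stops the trial, and SAP 3 says the Sponsor is doing so. For subjects still on treatment the two dates nearly coincide, so a programmer could slip from one to the other. One line naming the subject's own date would rule that out.

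Part of this stands. SAP 10.1 lacks the cross-reference, and closure censoring of early leavers would be wrong. But the line would only restate the later-of rule as the protocol's vocabulary already leads one to read it, and nothing suggests that closure was intended or programmed.

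Dropping the later-of clause and cutting back to the last assessment is no clear gain either. If events are known up to exit, it slightly overstates worsening (26.6% against 25.9% at the highest exit rate above). If nothing is captured after the last assessment, it is slightly closer to the truth than own exit.

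Nor does the rule conflict with SAP 8.2, which states "Missing data will not be imputed". Choosing a censoring date does not impute a value, and the question would arise only under closure.

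**Conclusion.** The concern does not hold as a fault in the plan. SAP 10.1 leaves out a detail that the protocol's own usage and the date in SAP 9.1 supply. An analyst who follows them censors each subject at the later of that subject's last worsening assessment and own exit, which is sound.

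On that reading the 3-year estimate is unbiased if events are known up to exit, and understated by at most about 1.0 point if every leaver carries six unobserved weeks. The 0.4 to 12.2 points under closure need both a reading that the documents do not support and, at the upper end, event-free exit of 0.25 per year. Exits for worsening or for a required prostacyclin are themselves events, so they do not add to that rate. At exit of 0.02 to 0.05 per year even closure costs 0.4 to 2.9 points, below the 5.7-point standard error.

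All rates are assumptions, with constant and independent hazards. Event counts and crude incidence are the same under either reading. Dropout linked to deterioration remains a limitation that neither choice of date would cure.

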10.3 WHO FUNCTIONAL CLASS

WHO FC information will be listed by treatment group in the parent study and will include the subject number, visit, assessment date (day), and WHO FC. The summaries of the WHO FC will be provided by treatment group in the parent study. The summaries will include descriptive statistics for measurements at each visit and the shift from baseline. Baseline is defined as the last WHO FC assessed prior to the first dose of ralinepag in the APD811-007 study.

10.4 HEMODYNAMICS

Right heart catheterization (RHC) measurements will be obtained at 1 year (± 3 months) after a subject enrolls into Study APD811-007. If the subject has been in Study APD811-007 beyond 1 year (± 3 months) at the time of regulatory/ethics approval of Protocol Amendment 2, an RHC assessment will be conducted at 2 years (± 3 months) instead. If a subject has been enrolled in Study APD811-007 more than 2 years at the time of regulatory/ethics approval, an RHC assessment will be performed at the time of those approvals.

Hemodynamic values will be listed by treatment group in the parent study. The summaries of the hemodynamic values will be provided by treatment group in the parent study. The summaries will include descriptive statistics for measurements at each visit and the change from baseline values. The summary statistics may include the geometric mean, interquartiles, and ratio to the baseline. Baseline is defined as the last hemodynamic values assessed prior to the first dose of ralinepag in the APD811-007 study. The mean plot of PVR may be generated across time with each parent treatment group.

10.5 BNP/NT-proBNP

BNP and NT-proBNP will be measured at Baseline and then every 3 months during the treatment period. BNP and NT-proBNP will be listed by treatment group in the parent study. The summaries of the BNP and NT-proBNP will be provided by treatment group in the parent study. The summaries will include descriptive statistics for measurements at each visit and the change from baseline values. The summary statistics may include the geometric mean, interquartiles, and ratio to the baseline. Baseline is defined as the last BNP and NT-proBNP assessed prior to the first dose of ralinepag in the APD811-007 study.

11 SAFETY ANALYSES

11.1 ADVERSE EVENTS

AEs are captured from the time the Informed Consent Form is signed. AEs that are ongoing at the parent study Termination Visit are recorded as continuing AEs in the APD811-007 study. All AEs with an onset date on or after the first dose of ralinepag in the APD811-007 study or AEs ongoing from the parent study will be included in data listings and summaries.

The AEs will be coded using the Medical Dictionary for Regulatory Activities, and all summaries will utilize the Preferred Term (PT) and/or System Organ Class (SOC). All AEs and serious adverse events (SAEs) will be organized by treatment group in the parent study and listed by subject number, including onset date (day) and time, stop date (day) and time, verbatim term, corresponding PT and SOC, seriousness, severity, relationship to study drug, action taken with study drug, and outcome.

The overall summary of AEs includes the number of subjects with any AE, the number of subjects with any study drug-related AEs, the number of subjects with AEs leading to study drug withdrawal, the number of subjects with any SAEs, the number of subjects with any severe AEs, and the number of subjects with any study drug-related severe AEs.

The summaries of AEs by SOC and PT will be provided by treatment group in the parent study and overall. The summaries of AEs, SAEs, severe AEs, AEs related to ralinepag, SAEs related to ralinepag, and AEs leading to permanent discontinuation of ralinepag will include the number (percent) of subjects and number of events for each reported PT.

The summary of AEs adjusted for length of ralinepag exposure will include the number (percent) of subjects and number of events for each reported PT, as well as the number of events per patient-years of exposure.

